#### 11.4. Week 4 +/- 1 Day (End of Week 4)

The following procedures will be performed:

- Assess and record concomitant medications;
- Assess and record Adverse Events;
- Targeted Physical Exam;
- Obtain subject weight in kilogram;
- Vital signs (blood pressure, respiratory rate, heart rate);
- Blood sample for central laboratory analysis including hematology, serum chemistry and eGFR;
- Urinalysis:
- Urine pregnancy test will be performed for all female subjects of childbearing potential;
- Collect unused study drug and bottles and evaluate compliance;
- Dispense study medication (4-week supply, 1 bottle of 60 capsules).

#### 11.5. Week 8 +/- 1 Day (End of Week 8)

- Assess and record concomitant medications:
- Assess and record Adverse Events;
- Targeted Physical Exam;
- Obtain subject weight in kilogram;
- Vital signs (blood pressure, respiratory rate, heart rate);
- Blood sample for central laboratory analysis including hematology, serum chemistry and eGFR;
- Urinalysis;

- Urine pregnancy test will be performed for all female subjects of childbearing potential;
- MDS-UPDRS;
- Collect unused study drug and bottles and evaluate compliance;
- Dispense study medication (8-week supply, 2 bottles of 60 capsules).

# 11.6. Week 16 +/- 3 days (End of Week 16)

The following procedures will be performed:

- Assess and record concomitant medications;
- Assess and record Adverse Events;
- Complete physical examination;
- Obtain subject weight in kilograms;
- Vital signs (blood pressure, respiratory rate, heart rate);
- Blood sample for central laboratory analysis including hematology, serum chemistry and eGFR;
- Urinalysis;
- Urine pregnancy test will be performed for all female subjects of childbearing potential;
- MDS-UPDRS;
- Collect unused study drug and bottles and evaluate compliance;
- Dispense study medication (12-week supply, 3 bottles of 60 capsules).

# 11.7. Week 28 +/- 3 days (End of Week 28)

- Assess and record concomitant medications;
- Assess and record Adverse Events;
- Targeted physical examination;
- Obtain subject weight in kilograms;
- Vital signs (blood pressure, respiratory rate, heart rate);
- Blood sample for central laboratory analysis including hematology, serum chemistry and eGFR;
- Urinalysis;
- Urine pregnancy test will be performed for all female subjects of childbearing potential;

- MDS-UPDRS;
- Collect unused study drug and bottles and evaluate compliance;
- Dispense study medication (12-week supply, 3 bottles of 60 capsules).

# 11.8. Week 40 +/- 3 days (End of Week 40)

The following procedures will be performed:

- Assess and record concomitant medications;
- Assess and record Adverse Events;
- Targeted physical examination;
- Obtain subject weight in kilograms;
- Vital signs (blood pressure, respiratory rate, heart rate);
- Blood sample for central laboratory analysis including hematology, serum chemistry and eGFR;
- Urinalysis;
- Urine pregnancy test will be performed for all female subjects of childbearing potential;
- MDS-UPDRS;
- Collect unused study drug and bottles and evaluate compliance;
- Dispense study medication (12-week supply, 3 bottles of 60 capsules).

# 11.9. Week 52 +/- 3 Days (End of Week 52)

- Assess and record concomitant medications;
- Assess and record Adverse Events;
- Complete physical examination including body weight (recorded in kilograms);
- Vital signs (blood pressure, respiratory rate, heart rate);
- Blood sample for central laboratory analysis including hematology, serum chemistry and eGFR;
- Urinalysis;
- Urine pregnancy test will be performed for all female subjects of childbearing potential;
- MDS-UPDRS;
- Collect unused study drug and bottles and evaluate compliance;
- Dispense study medication (12-week supply, 3 bottles of 60 capsules).

#### Week 64 +/- 3 Days (End of Week 64) 11.10.

The following procedures will be performed:

- Assess and record concomitant medications:
- Assess and record Adverse Events;
- Targeted physical examination;
- Obtain subject weight in kilograms;
- Vital signs (blood pressure, respiratory rate, heart rate);
- Blood sample for central laboratory analysis including hematology, serum chemistry and eGFR;
- Urinalysis;
- Urine pregnancy test will be performed for all female subjects of childbearing potential;
- MDS-UPDRS;
- Collect unused study drug and bottles and evaluate compliance;
- Dispense study medication (12-week supply, 3 bottles of 60 capsules).

#### 11.11. **Week 76 +/- 3 Days (End of Week 76)**

- Assess and record concomitant medications:
- Assess and record Adverse Events;
- Targeted physical examination;
- Obtain subject weight in kilograms;
- Vital signs (blood pressure, respiratory rate, heart rate);
- Blood sample for central laboratory analysis including hematology, serum chemistry and eGFR;
- Urinalysis;
- Urine pregnancy test will be performed for all female subjects of childbearing potential;
- MDS-UPDRS:
- Collect unused study drug and bottles and evaluate compliance;
- Dispense study medication (12-week supply, 3 bottles of 60 capsules).

#### Week 88 +/- 3 Days (End of Week 88) 11.12.

The following procedures will be performed:

- Assess and record concomitant medications:
- Assess and record Adverse Events;
- Targeted physical examination;
- Obtain subject weight in kilograms;
- Vital signs (blood pressure, respiratory rate, heart rate);
- Blood sample for central laboratory analysis including hematology, serum chemistry and eGFR;
- Urinalysis;
- Urine pregnancy test will be performed for all female subjects of childbearing potential;
- MDS-UPDRS;
- Collect unused study drug and bottles and evaluate compliance;
- Dispense study medication (12-week supply, 3 bottles of 60 capsules).

#### 11.13. Week 100 +/- 3 Days (End of Week 100)

- Assess and record concomitant medications:
- Assess and record Adverse Events;
- Complete physical examination including body weight (recorded in kilograms);
- Obtain subject weight in kilograms;
- Vital signs (blood pressure, respiratory rate, heart rate);
- Blood sample for central laboratory analysis including hematology, serum chemistry and eGFR;
- Urinalysis;
- Urine pregnancy test will be performed for all female subjects of childbearing potential;
- MDS-UPDRS;
- Collect unused study drug and bottles and evaluate compliance;
- Dispense study medication, if necessary.

# 11.14. Early Termination Visit

The following procedures will be performed:

- Assess and record concomitant medications;
- Assess and record Adverse Events;
- Complete physical examination including body weight (recorded in kilograms);
- Vital signs (blood pressure, respiratory rate, heart rate);
- Blood sample for central laboratory analysis including hematology, serum chemistry and eGFR;
- Urinalysis;
- MDS-UPDRS;
- Blood sample for serum pregnancy test in female subjects of childbearing potential;
- Collect unused study drug and bottles and evaluate compliance.

## 11.15. Safety Follow Up Visit

The following procedures will be performed:

- Assess and record concomitant medications;
- Assess and record Adverse Events;
- Targeted Physical Exam;
- Vital signs (temperature, blood pressure, respiratory rate, heart rate);
- Blood sample for serum pregnancy test in female subjects of childbearing potential.

## 12. ADVERSE AND SERIOUS ADVERSE EVENTS

During the study, the Investigator or study site personnel will be responsible for querying and recording adverse events (AEs) and serious adverse events (SAEs), as detailed in this section of the protocol. In this study AEs and SAEs will be reported from the time of study drug administration until the last study visit or death, whichever occurs first.

### 12.1. Definition of Adverse Events

An adverse event (AE) is any untoward medical occurrence that occurs in conjunction with the use of a medicinal product in humans, whether or not considered to have a causal relationship to the medicinal product. An AE can, therefore, be any unfavorable or unintended sign (including a clinically significant abnormal laboratory finding), symptom, or disease temporally associated with the use of a medicinal product, whether or not considered related to the medicinal product.

## 12.1.1. Adverse Event (AE)

Any medical condition or clinically significant laboratory abnormality with an onset date before the first date of study drug administration is usually considered to be pre-existing, and should not be documented in the CRF as an AE.

Any AE (i.e., a new event or an exacerbation of a pre-existing condition) with an onset date after study drug administration up to and including the designated follow-up safety visit should be recorded as an AE on the CRF. All AEs must be recorded on the AE CRF regardless of the severity or relationship to study medication. It is important that Investigators also report all AEs that result in permanent discontinuation of the study drug being studied, whether serious or non-serious.

### An AE does include:

- an exacerbation of a pre-existing illness;
- an increase in frequency or intensity of a pre-existing episodic event or condition;
- a condition detected or diagnosed after study drug administration even though it may have been present prior to the start of the study;
- persistent disease or symptoms present at baseline which worsen following the start of the study.

### An AE **does not** include:

- medical or surgical procedures (e.g., surgery, endoscopy, tooth extraction, transfusion) Note: in this case, the condition that led to the procedure is an AE;
- pre-existing diseases or conditions present or detected prior to start of study drug administration, which do not worsen;
- the disease or disorder being studied or a sign or symptom associated with that disease (i.e., signs or symptoms associated with lack of efficacy will generally be considered to reflect underlying disease, rather than AEs):
- situations where an untoward medical occurrence has not occurred (e.g., hospitalization for elective surgery, social, and/or convenience admissions);
- overdose of either study drug or concomitant medication without any signs or symptoms. (Dosing details will be recorded on the appropriate eCRF(s)).

The Investigator should attempt to establish a diagnosis of the event based on the signs, symptoms and/or other clinical information. In such cases, the diagnosis should be documented as the AE (and SAE if serious) and not the individual signs/symptoms.

All AEs must be fully and completely documented on the AE page of the CRF and in the subject's medical notes. The following attributes must be assigned: description of AE, dates and times of onset and resolution (or whether ongoing), severity (Section 12.1.2), causality to study drug (Section 12.2), whether an SAE or not (Section 12.1.4), and action taken (i.e., no action taken; study medication interrupted; study medication discontinued; other).

Page 50 of 74

In the event that a subject is withdrawn from the study because of an AE, it must be recorded on the CRF. The subject should be followed and treated by the investigator until the AE has resolved or a new chronic baseline has been established

The investigator must report all directly observed AEs and all spontaneously reported AEs. At each visit the investigator will ask the subject a nonspecific question (e.g., "Have you noticed anything different since your last visit?") to assess whether any AEs have occurred since the last report or visit. AEs will be identified and documented on the AE page of the CRF in appropriate medical terminology.

### 12.1.2. Severity of Adverse Events

The severity of each AE/SAE should be classified into one of three defined categories as follows:

- **Mild:** the AE is easily tolerated by the subject, causes minimal discomfort, and does not interfere in a significant manner with the subject's normal functioning level or activities;
- **Moderate:** the AE is sufficiently uncomfortable to interfere with normal everyday activities, but is not hazardous to health;
- **Severe:** the AE produces significant impairment of functioning or incapacitation and is a definite hazard to the subject's health.

These three categories are based on the investigator's clinical judgment, which in turn depends on consideration of various factors such as the subject's reports, the physician's observations, and the physician's prior experience. The severity of the AE should be recorded in the appropriate section on the AE page of the CRF.

The evaluation of severity must be distinguished from the evaluation of "seriousness" (see Section 12.1.4). A severe event might not meet the criteria for seriousness and a serious event might be evaluated as mild or moderate. For example, a subject might have a **severe** headache that does not require hospitalization and is consequently **not serious**; or a subject might have a **mild** myocardial infarction that requires hospitalization and is therefore **serious**.

### 12.1.3. Follow-up of Adverse Events and Serious Adverse Events

All AEs and SAEs must be followed until resolution (or return to baseline status), or until the condition stabilizes or is otherwise explained, or until the subject dies or is lost to follow-up. The Investigator is responsible for ensuring that follow-up includes any supplemental investigations as may be indicated to elucidate as completely as practical the nature and/or causality of the AE/SAE. This may include additional laboratory tests or investigations, histopathological examinations, or consultation with other health care professionals.

The sponsor may request that the Investigator perform or arrange for the conduct of supplemental measurements and/or evaluations. If a subject dies during participation in the study or during a recognized follow-up period, the Investigator should provide the Sponsor with a copy of any post-mortem findings, including histopathology.

### 12.1.4. Serious Adverse Event (SAE)

A serious adverse event (SAE) is any AE occurring at any dose that:

- results in death;
- is life-threatening (subject is at immediate risk of death at the time of the event);
- requires inpatient hospitalization or results in prolongation of existing hospitalization;
- results in persistent or significant disability/incapacity;
- is a congenital anomaly/birth defect in the offspring of a subject who received study drug;
- is a significant or important medical event, i.e., an event that, based upon appropriate medical judgment, may jeopardize the subject and may require medical or surgical intervention to prevent one of the above mentioned criteria (examples of such events are intensive treatment in an emergency room or at home for allergic bronchospasm, blood dyscrasias or convulsions that do not result in hospitalization, or development of drug dependency or drug abuse).

When a causality assessment is provided for an SAE, it is important to include a rationale for the assessment, so that a better understanding of the reported event can be compiled. The rationale should be accompanied by all available supporting evidence, including relevant laboratory tests, histopathology evaluations, and the results of other diagnostic procedures. The Investigator's rationale with supporting evidence is valuable when the Sponsor performs a cumulative analysis of similar events.

A Suspected Unexpected Serious Adverse Reaction (SUSAR) is any serious adverse event that is considered related to the investigational product, and that is also unexpected. SUSARs qualify for expedited reporting to applicable Health Authorities, Eudravigilance, and IRB/REB/IECs.

### 12.1.4.1. Clarification of SAE Definition

"Occurring at any dose" does not imply that the subject is receiving study drug at the time of the event. Dosing may have been interrupted temporarily prior to the onset of the SAE, but may have contributed to the event

"Life-threatening" means that the subject was at immediate risk of death from the event as it occurred. This does not include an event that might have led to death, had it occurred with greater severity.

Complications that occur during hospitalizations are AEs. If a complication prolongs hospitalization, it is an SAE.

"Inpatient hospitalization" does not imply that the subject must have had an overnight stay in the hospital. If the subject was admitted to the hospital for less than a day for the purpose of treatment or observation, the definition of "Inpatient hospitalization" is met. Brief treatment in an outpatient clinic or Emergency department does not constitute "inpatient hospitalization."

The term "severe" is often used to describe the intensity (severity) of a specific event (see Section 12.1.2); the event itself, however, may be of relatively minor medical significance (such as severe headache). This is not the same as "serious," which is based on event outcome or

Page 52 of 74

action criteria usually associated with events that pose a threat to a subject's life or functioning. Seriousness (not severity) serves as a guide for defining regulatory reporting obligations.

An SAE is considered "unexpected" if it is not listed in the Investigator's Brochure or is not listed at the specificity or severity that has been observed. It is the responsibility of the Sponsor to make this determination.

### 12.1.4.2. Clarification of Subject Deaths

All subject deaths (regardless of relationship to study drug) should be reported within 24 hours for subjects while on study protocol up to and including the safety follow-up visit. This should be recorded on the subject CRF and the SAE form.

Death is an outcome of an AE and not an AE in itself. All reports of subject death should include an AE term for the cause of the death unless the protocol provides other specific instructions (e.g., mortality related to underlying disease is an efficacy endpoint). For all reports in which an AE term is not provided (other than "Death"), follow-up for the cause of death will be required. Only in the rare occurrence that no verbatim description of an AE can be obtained from the investigative site, then "Death – Unknown Cause" will be used as the event term.

# 12.2. Relationship to Study Drug

The relationship or association of the AE/SAE to study drug will be characterized as "**related**" or "**not related**". An AE/SAE will be considered to be **not related** to the use of the study drug if any of the following criteria are met:

- An unreasonable temporal relationship between administration of the product and the onset on the AE (e.g., the event occurred either before, or too long after administration of the product for it to be considered product-related);
- A causal relationship between the product and the AE is biologically implausible (e.g., death as a passenger in an automobile accident);
- A clearly more likely alternative explanation for the AE is present (e.g., typical adverse reaction to a concomitant drug).

Adverse events will be considered "related" to the use of the study drug if none of the "not related" criteria are met.

The Investigator will use clinical judgment to determine the relationship of the AE/SAE to study drug. An AE/SAE may be related to the study drug, other concomitant medications, intercurrent illness, a procedure performed in the course of the study, or another reason. Among the potential etiologies, the investigator should make a determination based on the most likely causal relationship. Alternative causes, such as the natural history of any underlying diseases, concomitant therapy, other risk factors, and the temporal relationship of the event to the study drug should be considered. The Investigator will also take into account the Investigator's Brochure (or Prescribing Information, if applicable) in the causality assessment.

There may be situations when an SAE has occurred and the Investigator has minimal information to include in the initial report to the Sponsor. However, it is very important that the Investigator always makes an assessment of causality prior to transmission of the SAE report to the Sponsor, as the causality assessment is one of the criteria used when determining regulatory reporting

Page 53 of 74

requirements. The Investigator may change the causality assessment in light of follow-up information, by amending the SAE report accordingly.

# 12.3. Recording Adverse Events

Out of range clinical laboratory findings (e.g., clinical chemistry, hematology) or findings on other assessments (e.g., electrocardiogram, X rays, vital signs) per se are not reported as AEs. However, if the out of range finding that is deemed clinically significant or is associated with signs and/or symptoms must be recorded as an AE (and additionally as an SAE if it meets the criteria of being serious; see Section 12.1.4), as described above.

The Investigator should exercise medical and scientific judgment in deciding whether an out of range clinical laboratory finding or finding on other assessment is clinically significant. Usually, the abnormality should be associated with a clinically evident sign or symptom, or be likely to result in an evident sign or symptom in the near term, in order to be considered clinically significant. A clinically significant laboratory abnormality in the absence of clinical symptoms may jeopardize the subject and may require intervention to prevent immediate consequences. For example, a markedly low serum glucose concentration may not be accompanied by coma or convulsions, yet be of a magnitude to require glucose administration to prevent such sequelae.

# 12.4. Reporting Adverse Events

The Sponsor has requirements for reporting SAEs to both the local regulatory authority, other regulatory agencies, and Eudravigilance about the safety of a drug under clinical investigation. The Sponsor or designee must be notified within 24 hours once the Investigator determines that an AE meets the protocol definition of an SAE. The procedures for reporting serious adverse events are as follows:

- Complete the "Serious Adverse Event Report";
- Contact the pharmacovigilance staff member identified on the SAE Report Form and report the Serious Adverse Event within 24 hours of the Investigator's knowledge of the event;
- For fatal or life-threatening events, also fax copies of hospital case reports, autopsy reports, and other documents when requested and applicable.

The Sponsor or designee may request additional information from the Investigator to ensure the timely completion of accurate safety reports.

Any fatal or life-threatening events should also be reported immediately by telephone to the Sponsor's designee.

The Investigator, or responsible person according to local requirements, must comply with the applicable local regulatory requirements concerning the reporting of SAEs to all applicable regulatory authorities and IRB/REB/IECs.

### 12.4.1. Post-Study Reporting Requirements

All SAEs, regardless of cause or relationship, which occur from the time of study drug administration up to and including the safety follow-up visit, must be reported to the Sponsor or designee. If the Investigator learns at any time after a subject has been discharged from the study

Page 54 of 74

of an untoward medical occurrence that would have qualified as an SAE during the study, and such event is reasonably related to previous study drug exposure, the Investigator should promptly notify the Sponsor or designee.

### 12.4.2. Investigator Reporting Responsibility

When an investigative site receives an initial or follow-up notification of an SAE or other safety information (e.g., revised Investigator's Brochure) from the Sponsor, the responsible person, according to local requirements, must submit this information to the local IRB/REB/IEC and keep a copy in their files.

### 12.4.3. Pregnancy

A pregnancy is not an AE. If a subject becomes pregnant while enrolled in the study following administration of study drug, the Sponsor or designee must be notified within 24 hours of the Investigator learning of the pregnancy. Administration of study drug will be discontinued immediately and the subject will be followed through the outcome of the pregnancy. The Investigator will be required to complete a Pregnancy Information Form and fax the information to the Sponsor or designee.

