### Investigational product, dosage, mode of administration, and dosing regimen:

Subjects will be allowed to change their PD medications as needed and record updates on the Concomitant Medications case report forms. Use of amantadine (other than provided study drug) is not allowed during study participation.

Treatment	Week 1	Weeks 2 – 100	Week 101
ADS-5102	170 mg	340 mg	170 mg
	ADS-5102	ADS-5102	ADS-5102
	(1 x 170 mg capsule)	(2 x 170 mg capsules)	(1 x 170 mg capsule)

Capsules are to be swallowed intact, and can be taken with any nonalcoholic beverage, and with or without food. Dosing will continue through Week 101.

Subjects whose estimated GFR falls below  $50 \text{ mL/min/}1.73\text{m}^2$  (but is  $\geq 30 \text{ mL/min/}1.73\text{m}^2$ ), confirmed by repeat testing, should discontinue study drug after receiving a reduced dose of 170 mg ADS-5102 for one additional week. The additional week of dosing at a reduced dose will not be needed for subjects who discontinue study drug before Week 4.

Subjects whose estimated GFR falls below 30 mL/min/1.73m^2, confirmed by repeat testing, at any time during the study should discontinue study drug (without the additional week of dosing at a reduced dose).

Subjects who discontinue study drug will have an early termination visit that includes efficacy assessments and safety follow-up.

Page 11 of 74

**Duration of treatment:** Duration of subject participation will be up to 105 weeks and will include a 2-week (maximum) screening period and up to 101 weeks of open-label treatment, followed by a safety follow-up visit 2 weeks after completion of treatment.

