Subjects will be enrolled into the study at Visit 2 (Week 0, Baseline) and return to the clinic after 4, 8, 16, 28, 40, 52, 64, 76, 88 and 100weeks dosing. Subjects will receive a telephone reminder at the end of Week 1 to increase their dose during Week 2. At the Week 100 visit, subjects will be instructed to reduce their dose for 1 week, taking 1 capsule nightly at bedtime. The amount of available unused drug will be assessed during the Week 100 visit, and if a subject needs an additional bottle dispensed to cover 1 week of a reduced dose, they should be provided with a new bottle.

An efficacy assessment using the MDS-UPDRS will be completed at all study visits, beginning with the Screening Visit, with the exception of the Baseline/Week 0 visit & Week 4 visit. A safety follow-up visit will occur approximately 2 weeks following the completion of treatment. Women of childbearing potential will also have a pregnancy test performed at the early termination visit or 2 weeks following the completion of treatment at the safety follow up visit.

Subjects who discontinue study drug before Week 101 will have an early termination visit that includes MDS-UPDRS assessments and safety follow-up.

Subjects who discontinue study drug after Week 4 should receive a reduced dose of 170 mg ADS-5102 for one additional week. The additional week of dosing at a reduced dose will not be needed for subjects who discontinue study drug before Week 4.

Adverse events (AEs) will be recorded beginning with the first dose of study drug and will continue through the safety follow-up visit. Concomitant medications will be recorded throughout the study.

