#### 6.4. **Dose Adjustment Criteria**

Subjects who discontinue study drug after Week 4 should receive a reduced dose for one additional week before stopping study drug. The additional week of dosing at a reduced dose will not be needed for subjects who discontinue study drug before Week 4.

Subjects whose estimated GFR falls below 50 mL/min/1.73m^2, confirmed by repeat testing, (but is  $\geq 30 \text{ mL/min/}1.73\text{m}^2$ ) should discontinue study drug after receiving a reduced dose of 170 mg ADS-5102 for one additional week. The additional week of dosing at a reduced dose will not be needed for subjects who discontinue study drug before Week 4.

Subjects whose estimated GFR falls below 30 mL/min/1.73m^2, confirmed by repeat testing, at any time during the study should discontinue study drug (without the additional week at a reduced dose).

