### 7.5. Discontinuation of Study Medication

Subjects who discontinue study drug after Week 4 should receive a reduced dose for one additional week of ADS-5102 before stopping study drug. The additional week of dosing at a reduced dose will not be needed for subjects who discontinue study drug before Week 4.

Subjects should discontinue study medication if judged necessary by the investigator or sponsor, and reasons may include any of the following:

- Estimated glomerular filtration rate (eGFR) falls below 50 mL/min/1.73m^2, confirmed by repeat testing. (see Section 6.4)
  - NOTE:
  - Subjects whose eGFR falls below 30 mL/min/1.73m^2 while on study should discontinue study drug without the additional week at a reduced dose.
- Need to take a medication that is excluded or that may interfere with study measurements
- Intolerable or unacceptable AEs
- Positive pregnancy test

If the subject decides to discontinue study drug, they will have an early termination visit that includes efficacy assessments and safety follow-up.

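### Section 12.4.3 stops study drug at once in pregnancy, but the general reduced-dose-week rule in the Synopsis and Sections 6.1, 6.4 and 7.5 makes no exception for it

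*Protocol*

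**What the plan says.** Section 12.4.3 is the only place in the protocol that gives a dosing instruction written for pregnancy: "Administration of study drug will be discontinued immediately and the subject will be followed through the outcome of the pregnancy". It also requires the Sponsor or designee to be told within 24 hours, and a Pregnancy Information Form.

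The general stopping rule appears in four places. Section 7.5 puts it as "Subjects who discontinue study drug after Week 4 should receive a reduced dose for one additional week of ADS-5102 before stopping study drug", and Section 6.4 as "Subjects who discontinue study drug after Week 4 should receive a reduced dose for one additional week before stopping study drug". Section 6.1 and the Synopsis (Study Design) name the dose: "Subjects who discontinue study drug after Week 4 should receive a reduced dose of 170 mg ADS-5102 for one additional week". All four waive the extra week for subjects who stop before Week 4.

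Section 7.5 then gives a list of reasons, introduced by "Subjects should discontinue study medication if judged necessary by the investigator or sponsor, and reasons may include any of the following". One entry is "Positive pregnancy test", with no note attached. The eGFR entry does have a note: subjects whose value falls below 30 "while on study should discontinue study drug without the additional week at a reduced dose". The Synopsis dosing text makes the same exception ("at any time during the study should discontinue study drug (without the additional week of dosing at a reduced dose"), and so does Section 6.4. Section 6.1 has no exception by reason.

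**The concern.** Two instructions apply to the same event and lead to different dosing. Section 12.4.3 stops the drug that day. Section 7.5, read on its own, treats a positive test as one more reason for stopping that falls under the reduced-dose week.

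Three features make the second reading plausible for a careful site:

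- Section 7.5 is the section on stopping study medication, and 6.4 is the section on dose changes. The pregnancy instruction sits under adverse event reporting, and neither 7.5 nor 6.4 points to it.
- The authors saw that some reasons for stopping should carry no extra week, and wrote that for eGFR below 30. Leaving the pregnancy entry without a note suggests that it is not exempt.
- The lead-in to the 7.5 list makes stopping a matter of judgement, whereas 12.4.3 is unconditional.

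At stake is a week of avoidable dosing in a pregnant subject, or a deviation recorded against a site that followed 7.5 as written.

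**Working it through.** No sample size, power or error rate is involved. The check sets every statement of the rule beside Section 12.4.3 and then counts the doses and visits affected.

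**Step 1. Statements of the rule**

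| Place | Instruction on stopping after Week 4 | Exception by timing | Exception by reason | Reference to 12.4.3 |
|---|---|---|---|---|
| Synopsis | One more week at 170 mg | Before Week 4 | eGFR below 30 | None |
| 6.1 | One more week at 170 mg | Before Week 4 | None | None |
| 6.4 | One more week, reduced dose | Before Week 4 | eGFR below 30 | None |
| 7.5 | One more week, reduced dose | Before Week 4 | eGFR below 30 | None |
| 12.4.3 | Immediate stop in pregnancy | None | Not applicable | Not applicable |

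The only cross-reference in the 7.5 list is to Section 6.4, for eGFR. The other protocol text on pregnancy in subjects on treatment (Section 7.3, Table 6, and the visit lists in Section 11) covers testing only. No order of precedence between sections is stated.

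**Step 2. Doses at issue for one affected subject**

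- Under 12.4.3: 0 further doses.
- Under the general rule: 7 nights × 1 capsule × 170 mg = 1,190 mg, as a maximum.

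**Step 3. When a scheduled test could raise the conflict**

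Table 6 schedules urine pregnancy tests after baseline at Weeks 4, 8, 16, 28, 40, 52, 64, 76, 88 and 100, which is 10 tests. Those after Week 4 number 10 − 1 = 9. Eight of them (Weeks 8 to 88) fall under the early-stopping rule. The ninth, Week 100, comes when every subject is due the planned Week 101 taper, which is the same 7 × 170 mg. A positive result there conflicts with 12.4.3 through the planned schedule as well as through the general rule.

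These are counts of visits, not probabilities. A stop before Week 4 raises no conflict, because the extra week is waived.

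**Step 4. Can the event occur?**

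The protocol provides for it. Table 6 tests women of childbearing potential, 7.5 lists a positive test as a reason to stop, and the shell for SAP Table 1.1.2 has a row for it. The number of such women is not given, so an expected count cannot be computed.

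**The case against.** The strongest reply is that the protocol already gives a workable answer. Section 12.4.3 is specific and says *will*; the reduced-dose week is general and says *should*. On ordinary reading the specific instruction prevails, and nothing in 7.5 says in terms that a pregnant subject is to be tapered. The 24-hour notification stands in the same paragraph as the immediate stop, so a site that reports the pregnancy correctly will see the dosing instruction, and the Sponsor can correct any error within a day or so. Seven doses is therefore a worst case. Pregnancy is also excluded at entry in all three groups, and contraception is required of sexually active women who could conceive, so cases should be few.

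Most of this stands as a limit on likelihood. It does not remove the contradiction. A reader can let the specific rule prevail only after finding it, and neither 7.5 nor 6.4 leads there.

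Two smaller points are fair. Week 100 belongs partly to the planned taper, so the tests under the early-stopping rule proper are 8, with Week 100 as a separate case. Section 6.1 has no eGFR exception to extend, so the pregnancy sentence must be written there in full. In addition, the contents of Appendix A are not in the text available here, and a footnote there cannot be ruled out. It would not correct 7.5.

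**Conclusion.** The point holds. As written, Sections 6.1, 6.4, 7.5 and the Synopsis give a dosing instruction that contradicts Section 12.4.3 for a subject found pregnant after Week 4. The difference is 0 doses against at most 7 doses of 170 mg (1,190 mg) per affected subject, and 9 of the 10 scheduled post-baseline urine tests fall in the period concerned.

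This is an inconsistency in a subject-safety instruction and not a statistical error. It should be fixed, but it is of low frequency. The conclusion assumes only that a site may act on 7.5 or 6.4 without consulting 12.4.3. It makes no claim about fetal risk or about the risk of abrupt withdrawal, since the documents give no data on either.

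**What to change.** Add one sentence to Sections 7.5 and 6.4, next to the eGFR-below-30 exception, and to Section 6.1 and the Synopsis, written out in full in 6.1. For example: *A subject with a positive pregnancy test stops study drug at once and takes no reduced-dose week, including the planned Week 101 taper (see Section 12.4.3).* In 7.5, also place the cross-reference beside the pregnancy entry in the list, so that the judgement wording of the lead-in is not read as applying to it.

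If only one place can be changed, 7.5 matters most.

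The cost is one sentence in four places, by amendment or clarification letter. Sample size, visit schedule and planned analyses do not change.
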